Compared to healthy females, the breast cancer group displayed altered global brain network organization characterized by significantly decreased global clustering as well as disrupted regional network characteristics in frontal, striatal and temporal areas. Breast cancer survivors also showed significantly increased self-report of executive function and memory difficulties compared to healthy females. These results suggest that topological organization of both global and regional brain network properties may be disrupted following breast cancer and chemotherapy. This pattern of altered network organization is believed to result in reduced efficiency of parallel information transfer. This is the first report of alterations in large-scale functional brain networks in this population and contributes novel information regarding the neurobiologic mechanisms underlying breast cancer-related cognitive impairment¹⁵³⁻¹⁵⁴.

We thus propose to evaluate both chemotherapy-induced changes in structural and functional parameters by evaluating (a) differences in cerebral white matter integrity [fractional anisotropy (FA) and mean diffusivity (MD)] maps before and after treatment with COGNUTRIN by using magnetic resonance DTI; (b) we will perform resting state fMRI to determine changes in prefrontal executive functioning in breast cancer patients treated from baseline and post intervention with COGNUTRIN compared to placebo. To date, imaging studies have only focused on assessing structural and functional cognitive disruption induced by chemotherapy. The proposed study aims to replicate these findings and extend them by testing the proposed interventions ability to offset the changes in cognitive performance in breast cancer patients post chemotherapy treatment.

Subjects will be provided prepared, specific and consistent instructions over the intercom prior to start of MRI as follows: “Keep your eyes closed, relax, try not to move, try to stay awake and just let your thoughts wander.” All subjects will be imaged on a 3T scanner with an eight channel phased- array head coil. **Time in scanner for technician getting the imaging optimized for the patient is 5 minutes.**

The resting fMRI will be completed first prior to others. Resting FMRI data will be acquired (Bruno et al, 2012) while participants rest in the scanner with their eyes closed using a T2* weighted gradient echo spiral pulse sequence: relaxation time = 2000 msec, echo time = 30 msec, flip angle = 80° and 1 interleave, field of view = 220, matrix = 64×64, in-plane resolution = 3.125. Number of data frames that will be collected is 216. An automated high-order shimming method based on spiral acquisitions will employed to reduce field heterogeneity. To co register and normalize functional images with a standardized template, a high-resolution, 3 dimension inversion-recovery prepared fast spoiled gradient echo anatomical scan will be acquired: relaxation time: minimum, echo time: minimum, flip: 11 degrees, inversion time: 300 msec, bandwidth: +/-31.25 kHz, field of view: 24 cm, phase field of view: 0.75, slice thickness: 1.5mm, 125 slices, 256×256 at 1 excitation. **The total scan time is estimated at 10 minutes.**

A T1- weighted whole brain 3D-TFE (182 contiguous coronal slices; 250 x 250 mm² FOV; 4.6 ms TE; 9.7 ms TR; 1.2-mm slice thickness; 256 x 256 matrix; 0.98 x 0.98 x 1.2 mm³ voxel size). T2-weighted TSE (28 transversal slices; 230 x 184 mm² FOV; 4-mm slice thickness; 3,000 ms TR; 80 ms TE), and a FLAIR (28 transverse slices; 230 x 183 mm² FOV; 125 ms TE; 11,000 ms TR; 2,800 ms IR delay; 4-mm slice thickness; 256 x 256 matrix; 0.65 x 0.87 x 4 mm³ voxel size) will also be acquired to confirm absence of primary brain pathology as an exclusion criterion. **Scan time 10 minutes.**

A whole brain DTI SE-EPI (diffusion- weighted single shot spin-echo echoplanar imaging) will be acquired with the following scanning parameters: 68 contiguous sagittal slices, 112 x 109 matrix size, 220 x 220 mm² FOV, 4,956 ms TR, 55 ms TE, 2.5 parallel imaging factor, 2.2-mm slice thickness, 1.96 x 1.96 x 2.2 mm³ voxel size. Diffusion gradients will be applied along 45 noncollinear directions with a b-value of 800 s mm⁻². Additionally one nondiffusion-weighted (b ¼ 0) set of images will be acquired resulting in a **total scan time of 10.34 min.**

We anticipated a total scan time of 30-45 minutes for both structural and resting functional MRIs, including time to prepare subject.

8.1 Primary Endpoint

The primary efficacy endpoint is to generate effect sizes for changes in the number of impaired neuropsychological tests. The planned intervention period is three months. Neuropsychological outcomes will be examined using a 2 (group; COGNUTRIN, placebo) X 2 (time; baseline, three-months) repeated measures ANOVA to examine differences in the number of impaired neuropsychological tests. Age, premorbid cognitive functioning, depression and fatigue will be evaluated for association with neurocognitive performance and entered as covariates in statistical analyses if a marginally significant association ($p < .10$) is observed.

The primary safety endpoint is incidence and severity of AEs occurring during intervention with either COGNUTRIN or placebo. All AEs that are reported by the subject, detected during a visit, physical examination, or laboratory work-up will be recorded in the participant's medical record and recorded on the CRF. All AEs that occur after the informed consent is signed will be recorded on the AE CRF whether or not related to study agent.

The sample size proposed in the current protocol will not provide sufficient statistical power, but information regarding effect sizes will be gathered and used as motivation for future clinical trials. We estimate that a minimum evidence of improvement in cognitive function with the 3 month intervention as indicated by a score of 1 standard deviation or more above population norms on the Hopkins Verbal Learning Test – Revised, Controlled Oral Word Association Test, or Color Trails Test Part 1 or 2 will be considered adequate to justify progression to a larger study.

8.2 Secondary Endpoints

The secondary endpoint will be improvement in subjective cognitive functioning as well as structural and resting state functional changes in MRI.

In addition we will examine the role of the cytokines and anti-oxidant biomarkers as mediators of reductions in the number of impaired cognitive tests.

We will also examine if other factors such as fatigue, depression, physical and functional activities are affected by COGNUTRIN compared to placebo.

The sample size proposed in the current protocol will not provide sufficient statistical power, but information regarding effect sizes will be gathered and used as motivation for future clinical trials.

8.3 Off Agent Criteria

Participants may stop taking study agent for the following reasons:

- after completing the protocol-prescribed intervention
- at the discretion of the investigator
- AE or serious adverse events (SAE) requiring dose interruption
- inadequate agent supply
- noncompliance with study requirements
- medical contraindication.

8.4 Off Study Criteria

If the subject never took study medication (*e.g.*, does not meet eligibility criteria or withdraws consent prior to randomization) the only activity required to remove the subject from the study is to complete the Off Study CRF. If the subject was randomized to a treatment arm and received study medication, post-intervention procedures according to the schedule of events should be completed to the extent possible.

- not meeting randomization (eligibility) criteria
- the protocol intervention and any protocol-required follow-up period is completed
- experiencing an AE or SAE

- lost to follow-up
- taking a concomitant medication
- medical contraindication prohibiting further study participation
- discovery of a pre-existing condition not observed at baseline eligibility
- withdrawal of consent
- protocol non-compliance (*i.e.*, visit schedule, dose administration, *etc.*)
- at the discretion of the investigator
- death

Post-intervention procedures according to the schedule of events will be completed to the extent possible.

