6.5 Dose and Toxicity Management: We will ensure that our protocol and informed consent comply with FDA recommendations. In addition, we have planned monthly visits to monitor daily symptoms monitor and will perform an interview for adverse events, unusual symptoms, change in medical condition and concomitant medications use. Any abnormality observed will be communicated by the research coordinator to the study MD for evaluation and for continuation in the study. Subjects in the study will be dropped from study until which time the symptom is determined to be unrelated to the study agent as determined by the study MD. We will provide each subject with a 24- hour contact phone number and specific instruction on contacting the research team including the MD in this study. In addition, evaluation of safety in this subject population has been added as a specific aim of the trial with a formal comparison of safety between active and placebo arms, further illustrating our commitment to ensuring subject safety in this and future clinical trials.

A patient's treatment will be discontinued in any of the following circumstances: (a) Allergic reaction to product; (b) Dramatic change in stool frequency; (c) Start of other treatments that may cause malabsorption; (d) Request of patient of MD or patient; (e) Unusual symptoms reported during follow-up or other unusual symptoms or blood work results observed during the study period; and, (f) Persistent nausea not controlled with antiemetics. There are no reductions in the Cognutrin® dose. If adverse events occur that require holding Cognutrin ® (until etiology is determined), the dose will remain the same once treatment resumes. Any toxicities associated or possibly associated with Cognutrin ® treatment will be managed according to standard medical practice. Subjects will be assessed clinically for toxicity prior to, during intervention on a monthly basis and at end of intervention. If >grade III toxicity occurs because of Cognutrin ® at any time during the study, treatment with Cognutrin ® will be discontinued. We will also inquire about hypersensitivity to fish/and or shellfish and symptoms of atrial fibrillation at each visit. All subjects will be followed by their medical oncologists for their cancer treatment, using the routine surveillance guidelines as established by the Cancer Center during the study.

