Adverse events requiring delays or permanent discontinuation of Cognutrin® are listed in the table below:

Event	Action
Grade 1 & 2 constitutional, dermatological, gastrointestinal (GI), metabolic and pain symptoms Examples: Rash Allergic rhinitis, cough, bronchitis. Abdominal Pain Belching/Gas Nausea/Vomiting Diarrhea	No Action Required Inform MD Document event in research and medical record
Grade 3	Discontinue Cognutrin ®/Notify Study PI
Grade 4	Discontinue Cognutrin ®/Notify Study PI
Grade 2, 3, or 4 abnormal liver function tests ^{1,2} as determined by NCI CTC version 4.0	Discontinue Cognutrin ®/Notify Study PI and Monitor until it returns to normal

1. Tests used to monitor liver function include: albumin, total and direct bilirubin, alkaline phosphatase, AST, ALT, total protein, PT/PTT.)
2. In the event that PT/PTT is abnormal due to anticoagulant therapy, treatment and/or drug discontinuation will be at the discretion of the site investigator/MD.

Regardless of the reason for holding study drug treatment, the maximum allowable length of treatment interruption is 1 week. Interruption of intake of >1 week will result in discontinuance of subject from the study. Patients who have an ongoing Cognutrin ®-related Grade 3-4 or serious adverse event at the time of discontinuation from study treatment will continue to be followed until resolution of the event or until the event is considered irreversible by the study MDs.

In addition, a standard multivitamin/ mineral preparation will be provided free of charge during the study duration, to assure a consistent baseline intake of essential vitamins and minerals among all study participants during the study period and to encourage subjects from not using other supplements that may contain components of the study agents. Subjects in the treatment and placebo arms will be provided these multivitamin/mineral supplements and instructed to consume 1 tablet daily with the dinner meal.

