12.7 Evaluation of Response

All participants included in the study will be assessed for response to intervention, even if there are major protocol deviations. We estimate that a minimum evidence of improvement in cognitive function with the 3 month intervention as indicated by a score of 1 standard deviation or more above population norms on the Hopkins Verbal Learning Test – Revised, Controlled Oral Word Association Test, or Color Trails Test Part 1 or 2 will be considered adequate to justify progression to a larger study.

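### The off-study wording is inconsistent and can end follow-up when the agent is stopped, so the week-12 scores behind the pilot's effect size are not secured for every randomised patient

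*Combined protocol and SAP*

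**What the plan says.** **Leaving the study.** Section 8.4 lists off-study reasons that include "experiencing an AE or SAE" and "taking a concomitant medication", with no grade, relatedness or prohibited-drug qualifier. Section 6.5 adds two routes: "Interruption of intake of >1 week will result in discontinuance of subject from the study", and "Subjects in the study will be dropped from study until which time the symptom is determined to be unrelated to the study agent". Section 7.6 places a telephone call 7 (+/-3) days after the agent is discontinued and treats the subject as off study once the call is complete.

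**Staying in.** For listed grade 1 and 2 symptoms the table in section 6.5 says "No Action Required". Section 8.3 limits the adverse-event reason for stopping agent to "AE or serious adverse events (SAE) requiring dose interruption". Section 6.4 has all medications taken on study logged. Section 4.1 admits patients on endocrine therapy, section 4.2 accepts warfarin, and section 12.5.4 collects psychotropic use as a possible covariate.

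**Assessment and analysis.** Section 8.4 asks, as far as possible, for post-intervention procedures in randomised patients who received agent. Section 12.7 says "All participants included in the study will be assessed for response to intervention, even if there are major protocol deviations". Section 12.4 specifies a 2 (group) x 2 (time) repeated measures ANOVA. Section 12.2 plans 40 evaluable subjects without defining the term, and no missing-data method is given.

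**The concern.** The primary efficacy product of this pilot is an effect size for change in the number of impaired tests (sections 8.1 and 12.4). That change needs a baseline score and a week-12 score, and Table 1 schedules the cognitive battery at those two visits only.

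If stopping or interrupting the agent ends study participation, the patients who lose their week-12 score are selected by tolerability or adherence. Either can differ between active capsules and placebo. The estimate would then describe patients who tolerated and kept taking their capsules, not the two randomised groups, and it would pass in that form into the design of the next trial.

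**Working it through.** **1. The wording, side by side**

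| Topic | Leads off study | Points the other way |
|---|---|---|
| Adverse event | 8.4: any AE or SAE listed; 6.5: dropped pending a relatedness decision | 6.5 table: no action for listed grade 1-2 symptoms; 8.3: only an AE requiring interruption, and only off agent |
| Medication | 8.4: any concomitant medication listed | 4.1, 4.2: endocrine therapy and warfarin allowed; 6.4, 12.5.4: use recorded |
| Interruption | 6.5: more than 1 week ends study participation | 8.3: interruption is an off-agent matter |
| Non-compliance | 8.4: listed | 6.6: requirements are re-explained; 12.7: assessed despite major deviations |

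Read literally, the adverse-event threshold for leaving the study is lower than the one for stopping agent.

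**2. Timing for an early stopper (illustrative)**

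Suppose a patient stops at the end of week 5, day 35. The section 7.6 call falls between day 35 + 7 - 3 = 39 and day 35 + 7 + 3 = 45, after which the patient is off study. The week-12 window opens at day 84 - 7 = 77, which is 32 days later. Section 8.4 does not say whether its post-intervention procedures include the week-12 battery, or when they are done after early stopping.

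**3. The plan's own power figure**

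Inputs from section 12.4: interaction .23 (read as Cohen's f), alpha .05, stability .5, 20 per arm (N = 40), m = 2 time points. The noncentrality is lambda = f² x N x m / (1 - rho), with 1 and N - 2 degrees of freedom.

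- N = 40: lambda = 0.0529 x 40 x 2 / 0.5 = 8.464, power 80.9%. The stated 80% is reproduced.
- N = 36 (40 less the 10% loss in section 4.3): lambda = 0.0529 x 36 x 4 = 7.618, power 76.5%.
- N = 32 (20% loss, assumed): lambda = 6.771, power 71.2%.
- N = 28 (30% loss, assumed): lambda = 5.925, power 64.9%.

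Ending with 40 analysable patients at 10% loss needs 40 / 0.9 = 44.4, so 45 randomised.

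**4. Illustrative bias**

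The documents give no dropout by arm, so these inputs are assumptions. There is no true effect. In each arm the fraction d with the lowest values of a latent factor drops out, and that factor correlates r with cognitive change. The completers' mean change is r x phi(z_d) / (1 - d), where z_d is the standard normal d-quantile and phi the normal density. The ratio phi(z_d) / (1 - d) is 0.195 at d = 10%, 0.350 at 20% and 0.497 at 30%.

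| Dropout, active vs placebo | r = .3 | r = .5 |
|---|---|---|
| 10% vs 10% | 0 | 0 |
| 20% vs 10% | 0.3 x 0.155 = 0.05 SD | 0.5 x 0.155 = 0.08 SD |
| 30% vs 10% | 0.3 x 0.302 = 0.09 SD | 0.5 x 0.302 = 0.15 SD |

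A simulation under the same assumptions agrees. For scale, the standard error of a between-arm difference with 20 per arm is sqrt(1/20 + 1/20) = 0.32 SD of change.

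**The case against.** The strongest reply is that the protocol does separate the two events: section 8.3 covers stopping agent and section 8.4 covers leaving the study. Section 8.4 asks twice for post-intervention procedures, and elsewhere (7.7.13, 7.7.14, 9.1) the protocol uses post intervention for the month-3 specimens and imaging, so the battery may well be meant. That stands as a fair reading of intent. It leaves content and timing unstated, and the request is hedged.

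A reader might infer three stronger things that the documents do not support:

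- That any adverse event or any medication compels removal. The list in 8.4 has no lead-in saying subjects will be removed and may simply be a list of reasons. The eligibility and recording rules plainly keep medicated patients in.
- That 8.4 flatly contradicts 12.7. Assessment after leaving is left open, not forbidden.
- That the plan specifies a completers-only population. It does not. The restriction follows from how a classical two-time-point ANOVA handles a missing score, together with the absence of a missing-data rule.

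It is also fair to say that differential dropout is hypothetical, that the illustrated bias is below half of one standard error, and that section 8.1 already declares power insufficient. The bias should not be set against the .40 in section 12.4, which belongs to a one-tailed paired test and not to a between-arm contrast.

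**Conclusion.** The point holds as an inconsistency and a gap. The off-study wording conflicts with other sections. Followed as written, sections 6.5 and 7.6 can end participation before the only cognitive assessment after baseline, and nothing firm secures the aim of section 12.7. The planned ANOVA has no stated way to include a patient without a week-12 score.

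The size of any bias cannot be known from the documents. The 0.05 to 0.15 SD range rests on assumed dropout differences of 10 to 20 points and correlations of .3 to .5, and with equal dropout under the same mechanism it is zero. The loss of power from about 81% to 76.5% rests on the plan's own 10% loss and on those patients leaving the ANOVA. In a declared pilot this should be corrected, because the effect size is what it exists to deliver, but it does not invalidate the trial.

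**What to change.** 1. Reconcile sections 6.4, 6.5, 7.6, 8.3 and 8.4, and the non-compliance wording in 6.6. Which adverse-event, medication and interruption triggers apply is for the sponsor to decide.
2. State that stopping or interrupting the agent does not by itself end study follow-up. The week-12 cognitive battery, questionnaires and bloods, and MRI where safe, are sought at the scheduled time from every randomised patient who has not withdrawn consent.
3. In section 12.4, make the primary analysis all randomised patients as randomised, and define *evaluable* in 12.2. Use a likelihood-based mixed model or a baseline-adjusted analysis, with a missing-data sensitivity analysis.

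Step 2 matters most. With a single assessment after baseline, a mixed model gains only the dropouts' baseline scores, and ordinary ANCOVA still needs the week-12 score. Neither removes bias from unmeasured outcomes that differ after allowing for baseline.

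The cost is protocol wording, a revised model statement, and some additional week-12 visits by patients who stopped early.

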9 SPECIMEN MANAGEMENT

9.1 Blood Samples

All samples once drawn must be processed and stored appropriately until pick-up by the designated courier to transport to the Moffitt Cancer Center clinical laboratories. All safety labs will be forwarded to the Moffitt clinical labs in real time (CBC/CMP/PT/PTT). 2 - 10 ml tube will be forwarded to Tissue Core labs at the Moffitt Cancer Center for processing and storage. Once labs specimens for 40 subjects (pre and post intervention) have been collected, they will be transported from Tissue to [name] lab at USF and [name] lab at MCC by the clinical research coordinators, using appropriate containers to preserve the temperature and thus integrity of the specimens for assay of oxidative stress markers.

10 REPORTING ADVERSE EVENTS (AEs)

DEFINITION: An adverse event is any unfavorable and unintended sign (including an abnormal laboratory finding), symptom, or disease temporally associated with the use of a medical treatment or procedure that may or may *not* be considered related to the medical treatment or procedure. An AE is a term that is a unique representation of a specific event used for medical documentation and scientific analyses.

A list of AEs that have occurred or might occur (Reported AEs and Potential Risks) can be found in § 6.2, Pharmaceutical Information as well as the Investigator Brochure.

10.1 Adverse Events

10.1.1 Reportable AEs

All AEs that are reported by the subject, detected during a visit, physical examination, or laboratory work-up must be recorded in the participant's medical record and recorded on the CRF. All AEs that occur after the start of study agent must be recorded on the AE CRF whether or not related to study agent.

10.1.2 Data Elements

- AE reported date
- AE Verbatim Term
- CTCAE Term (v 4.0)
- Event onset date and event ended date
- Severity grade
- Attribution to study agent (relatedness)
- Whether or not the event was reported as a Serious AE (SAE)
- Action taken with the study agent
- Whether or not the subject dropped due to the event
- Outcome of the event
- Comments

10.1.3 Severity of AEs

Identify the AE using the NCI Common Terminology Criteria for AEs (CTCAE) version 4.0. The

CTCAE provides descriptive terminology and a grading scale for each AE listed. A copy of the CTCAE can be found at http://evs.nci.nih.gov/ftp1/CTCAE/CTCAE_4.03_2010-06-14_QuickReference_8.5x11.pdf

AEs will be assessed according to the CTCAE grade associated with the AE term. AEs that do not have a corresponding CTCAE term will be assessed according to their impact on the participant's ability to perform daily activities as follows:

Grade	Severity	Description
1	Mild	Asymptomatic or mild symptoms, clinical or diagnostic observations only; intervention not indicated
2	Moderate	Minimal, local or noninvasive intervention indicated; limited age-appropriate instrumental ADL*
3	Severe	Severe or medically significant but not immediately life-threatening; hospitalization or prolongation of hospitalization indicated; disabling; limiting self care ADL**
4	Life threatening	Life threatening consequences; urgent intervention indicated
5	Fatal	Death related to AE

* Instrumental ADL refer to preparing meals, shopping for groceries or clothes, using telephone, managing money, etc.

** Self care ADL refer to bathing, dressing and undressing, feeding self, using the toilet, taking medications, and not bedridden.

